Randomization will be stratified by developmental screenings result (high/moderate vs. low) as well as by clinic system, creating 8 groups that will be divided between the intervention and control groups to ensure even representation. To determine group assignment, the Research Assistant will enter the developmental screening result and clinic into REDCap, which will calculate the risk level as well as assign group. The Research Assistant will provide the participant with their group assignment at this time as well as describe briefly the intervention further for the intervention group. In addition, the Research Assistant will remind the participant that a summary of the results will be provided to their doctor.

Baseline Developmental Assessments:

The Research Assistant will then administer two developmental assessments over the phone: the Child Behavior Checklist (CBCL) and the PEDS:DM-Assessment Level (AL). The subdomains of the CBCL the RA will administer include: attention problems, aggressive behavior, autism spectrum problems, and oppositional defiant problems. All children will be asked all CBCL questions. The PEDS:DM-AL includes several subscales: fine motor, self-help, receptive language, expressive language, gross motor, social emotional, and academic. Together, they combine to form the cognitive overall score, which is used to calculate age equivalency. All low risk kids will receive the expressive and receptive language scale questions. Moderate and high risk kids will receive the full PEDS:DM-AL.

In addition, the RA will ask about families' experiences with care at the clinic and anticipatory guidance received; sociodemographic questions, including covariates such as child gender, parent education level, parent marital status, race/ethnicity, language, household composition and income, health insurance status, as well as a hunger scale and the PHQ2; a financial wellbeing scale, and the protective factors survey.

Engagement:

To keep families engaged and remind them of study participation over the 24-month period, parenting tips and child health information will be provided by text monthly – texts will be relevant to the full age range of the kids enrolled at any time point (11 months to 5 years) and will include topics such as sleep, screen time, safety, and nutrition. In addition, a reminder letter asking for updated contact information will be sent 1-2 months prior to each survey time point. A

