In all children, linear regressions will be used to compare PEDS:DM-AL language subscale scores in each arm. In the subset of children who screened positive and therefore received the full PEDS:DM-AL (Parents' Evaluation of Developmental Status: Developmental Milestones - Assessment Level), linear regressions will be used to compare each of the subscale scores in each arm. Since we will have baseline and 2-year follow-up PEDS:DM-AL scores, we will use change from baseline scores as outcomes, allowing us to compare change in the intervention group against change in the comparison group.

We will also conduct exploratory secondary analyses, each with probative value but less certain power. Since we will have scores measured at baseline and 1-year and 2-year follow-ups, we will be able to conduct longitudinal analyses, with multiple observations clustered within individuals using linear mixed models with random child effects. These models will adjust for

socio-demographic variables. The outcome variables will be appropriately transformed prior to fitting the model as needed.

The mixed effects models described above allow us to make statistical inference using all observed data, with the assumption of data missing at random. To assess the robustness of this analysis with respect to missing data, multiple imputation with pattern mixture models will also be used to impute missing data due to missed visits or loss to follow-up. For example, as a sensitivity analysis, we will assume that the distribution of missing data from missed visits or loss to follow-up is similar with that of the usual care group.

Secondary outcomes will include CBCL, family-centered care, and satisfaction scores. We will conduct longitudinal analyses like those for the language subscales. Also, sensitivity analyses clustering children by provider will be performed to assess robustness of findings to potential contamination by provider.

Hypothesis 3: Intervention costs per child screened will be exceeded by the societal value of the long-term benefits from 211-based care coordination.

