We will compare costs per child screened to benefits. Total costs will be disaggregated into RA screening/initial referral, 211 program, and diagnostic and developmental services costs. Total benefits will be disaggregated into income and value of life expectancy gains. Using evidence from literature, these benefits will be estimated by predicting changes in educational achievement from improvements in early life assessments (Aim 2 findings), then predicting changes in educational attainment from changes in educational achievement, and then predicting changes in lifetime income and life expectancy from changes in educational attainment. Sensitivity analyses will explore alternative assumptions about costs, relationships between early-childhood development and long-term outcomes, and value of a life-year.

Power Analysis

Given our planned RCT enrollment of 662 families (331 per group), and assuming loss to follow-up of 20% per year, we expect 424 families (212 per group) to complete the study. For each hypothesis, we report minimally detectable differences using study completers. These estimates are likely conservative, since some analyses will be performed using data collected prior to the end of follow-up and including >424 families. The enrollment sample size was chosen so that detectable differences would be within the bounds of the confidence intervals from the pilot data. Unless otherwise noted, reference rates were estimated from the pilot study.

Hypothesis 1: A higher proportion of families in the intervention group will a) be successfully referred to early childhood service organizations for evaluation, b) be deemed eligible for services by service organizations, and c) receive services, than families in the usual care group.

a) A sample size of 212 per group provides 80% power to detect a 11.9 percentage-point difference in the referral rate, assuming a reference rate of 20.4%, a chi-squared test, and an alpha of 0.05. This difference is smaller than observed in the pilot study (21.8 percentage points; 95% CI: 9.1-33.8).

b) A sample size of 212 per group provides 80% power to detect an 9.2 percentage-point difference in the eligibility rate, assuming a reference rate of 8.6%, a chi-squared test, and an alpha of 0.05. This difference is smaller than observed in the pilot study (14.3 percentage points; 95% CI: 5.6-24.0).

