c) A sample size of 212 per group provides 80% power to detect a 8.7 percentage-point difference in the service receipt rate, assuming a reference rate of 7.2%, a chi squared test, and an alpha of 0.05. This difference is smaller than observed in the pilot study (11.7 percentage points; 95% CI: 3.4-21.0).

Hypothesis 2: Over time, formal developmental assessment scores in the intervention group will improve more than scores in the usual care group.

Meta-analyses of interventions studies have shown a range of effect sizes (Cohen's d), from 0.3-0.8 for speech and language therapies, and 0.3-1.19 for Autism Spectrum Disorder. A sample size of 212 per group provides 80% power to detect an effect size as small as 0.27 on the PEDS:DM-AL, assuming a two-sample t-test, and a two-sided alpha of 0.05.

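### Hypothesis 2 makes nine PEDS:DM-AL comparisons with no lead outcome, order or adjustment, its power statement covers one test, and the estimate that feeds Aim 3 is not named

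*Combined protocol and SAP*

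**What the plan says.** The Hypothesis 2 text of the Statistical and Data Analysis Plan has two parts. In all children, linear regression compares the PEDS:DM-AL language subscales between arms. In the screen-positive subset, "linear regressions will be used to compare each of the subscale scores in each arm". The outcome in both is the change from baseline to two years.

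Baseline Developmental Assessments lists seven subscales, two of them language (expressive and receptive). Low-risk children get only those two; moderate- and high-risk children get the full instrument. Of the seven subscales it says: "Together, they combine to form the cognitive overall score, which is used to calculate age equivalency". The Hypothesis 2 analysis text does not mention that overall score.

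The Power Analysis for Hypothesis 2 states: "A sample size of 212 per group provides 80% power to detect an effect size as small as 0.27 on the PEDS:DM-AL". The basis it gives for this is a single unadjusted comparison at the two-sided 0.05 level. It names neither a scale nor a population. The 212 comes from "planned RCT enrollment of 662 families (331 per group") and 20% annual loss.

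The Hypothesis 3 text builds the benefit estimate by "predicting changes in educational achievement from improvements in early life assessments (Aim 2 findings") and does not say which finding.

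**The concern.** The longitudinal models are labelled exploratory, and CBCL, family-centered care and satisfaction are labelled secondary. The nine change-score comparisons carry no such label, so they stand together as the main test of Hypothesis 2. With no lead, order or success rule, the plan does not say what result would confirm or refute the hypothesis. Any one of nine nominally significant results could be presented as support, while the power statement describes a single test.

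The same gap carries into Aim 3. If the estimate for the benefit model is chosen after the results are seen, the choice could favour a large one, and the benefit would then be biased upward. The Aim 3 sensitivity analyses cover costs, the links from early development to later outcomes, and the value of a life-year. They do not cover which Aim 2 estimate enters.

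**Working it through.** **Inputs from the documents.** 662 enrolled, 1:1; 20% loss per year for two years; 212 completers per arm; two-sided alpha 0.05 (stated only in the power section); d = 0.27; seven subscales, two of them language.

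**Inputs assumed.** The documents give neither the correlation between subscales nor the screen-positive share. I use a common correlation ρ from 0 to 0.9 and a share f of 30%, 45% or 60%.

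**1. The plan's own figure.** Completers: 662 × 0.8 × 0.8 = 423.7, that is 424, or 212 per arm. Detectable effect for one test: (1.960 + 0.842) × √(2/212) = 2.802 × 0.0971 = 0.272. The noncentral t gives 0.273, and power at d = 0.27 is 79%. The stated 0.27 reproduces, for one unadjusted test in all completers.

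**2. Number of comparisons.** 2 in all children + 7 in the subset = 9.

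**3. Upper bound.** Nine independent tests would give 1 − 0.95⁹ = 37.0%. This cannot be reached, because the two all-children language comparisons contain the subset's own language data.

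**4. Nested simulation under no effect.** The seven subset statistics share correlation ρ. The two language statistics in low-risk children share the same ρ and are independent of the subset. The all-children statistic is √f × (subset) + √(1−f) × (low-risk). Standard errors in SD units are √(2/212) = 0.097 for all children and √(2/n) for the subset. The subset has n = 64, 95 or 127 per arm (212 × f), so its standard error is 0.177, 0.145 or 0.125. Ranges in the table run over f = 30-60%.

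| ρ | Any significant, either direction | Any significant, favouring intervention | Expected largest null estimate (SD) |
|---|---|---|---|
| 0 | 34-36% | 19-20% | 0.17-0.24 |
| 0.5 | 27-29% | 13-14% | 0.13-0.18 |
| 0.7 | 21-23% | 11-12% | 0.10-0.15 |
| 0.9 | 15-16% | 7-8% | 0.07-0.11 |

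A single two-sided test at 0.05 would give 5% and 2.5% in the first two result columns.

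**5. What the overall score could carry.** It exists only for moderate- and high-risk children. With 64, 95 or 127 per arm, one test at two-sided 0.05 has 33%, 46% or 57% power at d = 0.27, and the detectable d is 0.50, 0.41 or 0.35.

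**6. Splitting alpha instead.** At 0.05/9 = 0.0056 per test, the detectable d in all children rises to 0.353 and power at d = 0.27 falls to 50%. At 0.05/2 = 0.025 for the two language subscales, these become 0.300 and 70%.

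**The case against.** Several counter-arguments have force.

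- Hypothesis 2 is directional, so the relevant error is a false result in favour of the intervention, which is about half the two-sided figure. This stands, and both figures are given.
- The plan puts language in all children first and models its secondary analyses on the language subscales, which suggests an implicit lead of two tests. Those two alone would carry an error of about 8-10% (ρ from 0.7 to 0). The text leans that way but does not say so, and the seven subset comparisons are not marked as secondary.
- The overall score is not an obvious omission, since low-risk children cannot have it. This stands: it cannot lead in all children.
- The per-comparison level of 0.05 is inferred, because the analysis section states no test level. It is the only level given for this hypothesis.

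A reader might infer that the sponsor means to feed the best subscale into Aim 3. The documents do not say that. They leave the input unspecified, and several scores could enter.

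A reader might also extend the point to Hypothesis 1, whose Power Analysis lists "a) be successfully referred to early childhood service organizations for evaluation, b) be deemed eligible for services by service organizations, and c) receive services". The documents do not support a gatekeeping demand there. The analysis section lists only referral and receipt. The components are stated as separate claims, for which testing each at 0.05 is defensible. Gating would also bar a confirmatory claim on service receipt whenever referral missed.

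**Conclusion.** The concern holds for Hypothesis 2 and for the Aim 3 input. Nine unranked comparisons carry a chance of about 15-36% of at least one nominally significant result in either direction when there is no effect, and about 7-20% in favour of the intervention. If the largest estimate were used in Aim 3, its expected value with no effect would be about 0.07-0.24 SD, against a stated detectable effect of 0.27. All of these figures rest on the assumed correlation (0.9 to 0) and screen-positive share (30-60%).

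Two stronger readings are tempting and should not be used. The 37% for nine independent tests ignores the overlap between the all-children and subset language data. Scaling the selection bias with 212 per arm throughout is also wrong, because seven of the nine comparisons use only the subset. The stated 0.27 is itself correct for one test in all completers; what is missing is which test it describes.

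**What to change.** Before outcomes are compared by arm, amend the analysis plan as follows.

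1. Name one lead Hypothesis 2 outcome in all children and test its two-year change at two-sided 0.05. It can be one of the two language subscales, or their mean. The documents define no combined language score, so the mean would need a scoring rule.
2. Only if that result is significant, test the overall score in screen-positive children at two-sided 0.05. State that this test uses the subset alone, that the 0.27 figure does not apply to it, and that its power at d = 0.27 is about 33-57% for an assumed 30-60% share.
3. Report the remaining subscales with confidence intervals, as descriptive.
4. Name in advance which estimate, in which population, enters the Aim 3 benefit model.

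The fixed order splits no alpha, so the lead test keeps 212 per arm and a detectable effect of 0.27 in SD units of the chosen outcome. No added participants or data collection are needed; the work is plan wording, plus a scoring definition if the mean is chosen. The downside is that a single significant subscale can no longer be claimed as confirmatory, nor can the overall score if the lead outcome fails.

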Given that the intervention being tested requires parent adherence to recommendations (e.g., communicating with 211LA, keeping referral and service appointments) to achieve success, we will use an intention-to-treat analysis. Our analyses will be based on measuring differences between the intervention and comparison groups with respect to the above outcome variables. Additionally, covariate-adjusted differences will be evaluated using multivariable regression models. Incomplete variables will be handled using a multiple imputation approach with 10 imputations for multivariable analyses; imputations will be based on an iterative Markov chain Monte Carlo method, with initial values generated by an expectation–maximization algorithm. Finally, secondary analyses for all outcomes will include group*developmental screening risk category (low, moderate, high), or group*gender (female, male) interactions to explore differential intervention effects.

Hypothesis 1: A higher proportion of families in the intervention group will a) be successfully referred to early childhood service organizations for evaluation, and b) receive services, than families in the usual care group.

We will use multivariable logistic regression models for each of these binary outcome variables with group assignment as the main predictor, controlling for socio-demographic variables.

Secondary analyses will use the fact that multiple types of services may be indicated. This will allow us to examine specific services in isolation as binary outcome variables in logistic regressions. It is possible that certain types of services are more likely to be recommended or taken up than others. It is also possible that receipt of any vs. no services is too crude to distinguish among different types or severities of developmental needs. Thus, examining specific services may prove to be important adjunct analyses.

Hypothesis 2: Over time, formal developmental assessment scores in the intervention group will improve more than scores in the usual care group.

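### The main Hypothesis 2 regression of change does not name the baseline score or the randomization factors as covariates; adding them would usually gain precision at small cost

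*Combined protocol and SAP*

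**What the plan says.** All references are to the combined protocol and SAP.

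- **Hypothesis 2, main analysis** (Statistical and Data Analysis Plan). Language subscale scores are compared by arm in all children with linear regressions. A second strand, which opens "In the subset of children who screened positive and therefore received the full PEDS:DM-AL", compares every subscale by arm. For both, the plan says "we will use change from baseline scores as outcomes, allowing us to compare change in the intervention group against change in the comparison group". No covariate is named.
- **Hypothesis 2, longitudinal models.** Mixed models using baseline, 1-year and 2-year scores are planned, but as exploratory analyses. The only adjustment they name is for socio-demographic variables.
- **General paragraph of the analysis plan.** "covariate-adjusted differences will be evaluated using multivariable regression models", as an addition to the group comparison and without a list of covariates. Screening risk appears as a model term only in secondary interaction analyses.
- **Hypothesis 1.** Logistic models "with group assignment as the main predictor, controlling for socio-demographic variables".
- **Randomization.** "Randomization will be stratified by developmental screenings result (high/moderate vs. low) as well as by clinic system". Clinic system is not mentioned again in the analysis plan.
- **Baseline Developmental Assessments.** The one list labelled as covariates begins "covariates such as child gender, parent education level, parent marital status, race/ethnicity, language, household composition and income". It names no developmental score, risk level or clinic.
- **Power Analysis, Hypothesis 2.** 80% power for an effect size of 0.27 with 212 per group, from a two-sample t-test at two-sided alpha 0.05.

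**The concern.** A change score fixes the slope of follow-up on baseline at 1. Analysis of covariance (ANCOVA) estimates that slope from the data, so in large samples it is never less precise than the change score and is often clearly more precise. The baseline score is collected in every child for the language scales and in every screen-positive child for the full instrument. On the plan as written, the main analysis makes only partial use of it. The two factors that governed allocation are likewise not named in any main model.

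The margin is thin. The Power Analysis cites effect sizes from 0.3 upward, against a detectable 0.27 with all expected completers. The full set of subscales is available only in the screen-positive children, where numbers are smaller. The Hypothesis 2 estimates also feed the benefit side of the Hypothesis 3 cost comparison.

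**Working it through.** **Inputs from the documents.** 331 per group enrolled, 20% loss per year, 212 per group completing, effect size 0.27, 80% power, two-sided alpha 0.05 (Power Analysis). Eight strata from two risk levels and four clinic systems (Randomization).

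**Assumptions, not in the documents.** Baseline to follow-up correlation ρ; ratio k of follow-up SD to baseline SD; 40% of children screening positive.

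**1. The plan's own figures.** Completers: 331 × 0.8 × 0.8 = 211.8, or 212. With 212 per group a two-sample t-test has 79.2% power at 0.27, and the effect detectable with 80% power is 0.273. The stated figure reproduces. The plan does not say what SD the 0.27 is measured in; below it is read in SDs of change.

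**2. Variances.** Set the follow-up SD to 1 and the baseline SD to 1/k.

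- Change score: 1 + 1/k² − 2ρ/k
- ANCOVA: 1 − ρ²
- Difference: (1/k − ρ)², which is never negative and is zero when ρk = 1

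With equal SDs (k = 1) the ratio of ANCOVA to change-score variance is (1 − ρ²)/(2 − 2ρ) = (1 + ρ)/2.

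**3. Cost of the extra terms.** Uninformative covariates inflate the variance by about (N − 3)/(N − 3 − q). The calculation charges for q = 6: baseline score, risk, three clinic terms and baseline age. At N = 424 this is 421/415 = 1.014. In the subset, 0.40 × 424 is about 170 children (85 per arm), and the factor is 167/161 = 1.037.

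**4. Net result with equal SDs.**

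| ρ | Gross ratio | Net ratio, N = 424 | Detectable effect (0.273 now) | Power at 0.273 (80% now) | Net fall in variance, N = 170 |
|---|---|---|---|---|---|
| 0.3 | 0.65 | 0.66 | 0.221 | 93.2% | 33% |
| 0.5 | 0.75 | 0.76 | 0.238 | 89.5% | 22% |
| 0.7 | 0.85 | 0.86 | 0.253 | 85.5% | 12% |
| 0.9 | 0.95 | 0.96 | 0.268 | 81.4% | 2% |

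Simulation of the six-term model (10,000 runs, 212 per arm) gave power of 93.1, 90.3, 85.4 and 81.0%, and type I error of 4.8% at ρ = 0.5.

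**5. Net ratio with unequal SDs, N = 424.**

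- k = 0.7, ρ = 0.3/0.5/0.7/0.9: 0.42/0.47/0.50/0.41
- k = 1.25, ρ = 0.7 and 0.8: 0.995 and 1.014 (1.017 and 1.037 at N = 170)
- k = 1.5, ρ = 0.3/0.5/0.7/0.9: 0.88/0.98/1.01/0.79

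The worst case is ρk = 1, where only the cost in step 3 remains: 1.4% at N = 424 and 3.7% at N = 170.

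**6. Hypothesis 1.** Adding risk and clinic terms to a logistic model with an assumed 14 socio-demographic terms was simulated (10,000 runs per scenario, 40% screen positive). For referral, with assumed control rates of 39% v 8% by risk, type I error moved from 3.8% to 5.7% and power from 81.0% to 85.9%. To compare at equal size, add the normal quantile for power to the critical value implied by the observed type I error, then subtract 1.96:

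- Without strata: 2.075 + 0.878 − 1.96 = 0.993, power about 84.0%
- With strata: 1.903 + 1.076 − 1.96 = 1.019, power about 84.6%

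The gain is about 0.6 points. It is about 0.3 points in the two scenarios with weaker risk effects, and none for service receipt (about −0.8 and −0.2). Expected service-receipt events are 212 × (0.072 + 0.159) = 49.

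**The case against.** The strongest reply is that nothing in the plan fails. The change score is unbiased under randomization, it matches the hypothesis that scores will improve more, and the trial reaches about 80% power under the analysis it planned. This stands: a reader might infer bias or an invalid test, and the documents do not support that.

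The omission is also partly silence. Adjusted analyses are promised, the covariate list is open, and a linear regression can carry a baseline term. A reader might infer that the plan excludes baseline; it only fails to name it. The exploratory mixed models may recover part of the precision, and provider-clustered sensitivity analyses are planned, but neither is the main analysis.

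The size of the gain is unknown. Every ρ and k above is assumed, and children aged 11 to 42 months are re-measured two years later, so equal SDs cannot be taken for granted. At k = 1.25 and ρ of 0.7 to 0.8 there is essentially no gain. If 0.27 is in follow-up SDs instead, power for change against ANCOVA (equal SDs, baseline term only, cost of terms ignored) is 65.2% v 83.0% at ρ = 0.3, 79.4% v 89.4% at 0.5 and 94.8% v 97.3% at 0.7.

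Three further readings are tempting and do not hold.

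- The proportional gain is not larger in the screen-positive subset. It is slightly smaller, because the terms cost more there.
- The simulated rise in Hypothesis 1 power is not mainly real. Most of it comes from higher type I error.
- The words "which is used to calculate age equivalency" do not establish a need to adjust for age. They describe the overall cognitive score, whereas Hypothesis 2 analyses subscales whose metric is not given.

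**Conclusion.** The point holds as a recommended efficiency improvement, with medium confidence. The main Hypothesis 2 regression should name the baseline score and the randomization factors. With equal SDs there is a net gain at N = 424 unless ρ exceeds about 0.97 (2 × 415/421 − 1). In general the gain depends on how far ρk lies from 1, which the documents do not settle. The balance is favorable: a possible fall in variance of 14% to 34% at ρ of 0.7 to 0.3 with equal SDs, against a loss of at most about 1.4% in the full sample or 3.7% in a subset of 170. Most of the gain comes from the baseline score; the strata mainly align the analysis with the allocation.

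For Hypothesis 1 the case is narrower. Including the strata matches the analysis to the stratified randomization and can bring a conservative test back to about 5%. It should not be presented as a material power gain.

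**What to change.** **Hypothesis 2.** Specify the primary model as the 24-month score regressed on group, baseline score, risk stratum and clinic system. In the screen-positive subset the stratum is constant, so use moderate v high risk instead. Baseline age is optional. If Y = a + τG + βB, then Y − B = a + τG + (β − 1)B, so τ is identical with either outcome and can still be reported as a difference in change.

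**Hypothesis 1 (secondary).** Add risk stratum and clinic system to the logistic models. For service receipt keep the covariate list short: 49 events over 19 terms is 2.6 per term. Report a standardized risk difference beside the odds ratio, because the adjusted odds ratio is conditional on the strata and its interval need not narrow.

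**Cost.** SAP wording only; every variable is already collected. Without age there are five terms, and the factor is 421/416 = 1.012 at N = 424 and 167/162 = 1.031 at N = 170. With all six terms the subset cost is 3.0%, 3.7% or 5.0% if 50%, 40% or 30% of children screen positive.
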